- **MRI score:** Multi-parametric MRI Likert scale 1-5 where >3 indicates aggressive cancer.
- **BCR:** PSA $\geq 0.2\text{ng/ml}$ at any time post-RP and remaining at this level or further increase afterwards without further treatment (see Table 4 for endpoint definitions)
- **Post-RP treatment failure:** (see Table 4 for endpoint definitions)

2). Sample size

The study hypothesis is that the presence of CTCs has close to 100% sensitivity and specificity for micro-metastasis, and thus RP treatment failure. Due to the long-term nature of recurrence events, there will be a proof of principle part to this study which occurs within the funded study timeframe of 5 years, and an intention to collect and analyse relevant longer-term events at 10 years (see section 4 for objectives and endpoints). The primary endpoint is **post-RP treatment failure**, the majority of which will be due to BCR. Despite the long-term nature of events of interest, it will be possible to provide a timely estimate of sensitivity, since of those who do have an observable BCR event, most if not all are expected to have a positive CTC result. Thus, consistent with previous work, this study estimates predicting post-RP cancer events with 95% sensitivity. During the first 4.5 years of follow up, the hypothesised prevalence of BCR events to be at least 40%.

In order to confirm an expected sensitivity of 95% within 5% precision either side of a 95% confidence interval (CI) in a sample with an underlying prevalence of 40%, requires at least 73 events, that is at least 183 recruited individuals. Inflate this by 8.5% to a target recruitment of 200 to ensure suitability of samples and measurable outcomes.

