The recruitment plan will be 200 patients in the first two years of the 5-year project to allow an approximate 3.5 to 4 year median follow up. Specificity is important considering the future circumstance of potentially denying patients curative surgery, if a CTC test indicates metastasis. A study size of 200 and 120 true negatives would give a 97.5% lower confidence limit on a specificity of 99% (1% false positive rate). However, it is anticipated the specificity will be low due to positive results for those who recur beyond the 5-year study. Assuming these events are due to micro-metastases at the time of surgery, observed sensitivity and specificity will be used, plus additional analyses assuming up to 20% of the events occur after the funded 5-year project⁴⁻¹¹ to estimate the real false positive and negative rates.

3). Method of analysis

Study flow and patient characteristics will be reported. Measures of accuracy will be presented with 95% confidence intervals (CIs). The primary analysis is the estimation of the sensitivity of the pre-surgery existence of CTCs for detection of RP treatment failure, i.e. BCR or progression detected by any imaging at the 4.5-year follow-up time point. Observed specificity, positive and negative prediction values will also be reported at 4.5 years of follow up, with a note to indicate that these estimates are subject to change given the long-term nature of recurrence events. Specificity will be presented over time and additional analysis accounting for artificial inflation of false positives based on increasing prevalence of events. BCR-free survival will be estimated and Kaplan-Meier curves presented.

The number of participants with recorded metastases, lymph node metastases, deaths from any cause and PCa deaths during the first 4.5 years of follow up

Protocol for spin off research project- Circulating tumour cells as biomarkers to predict prostate cancer metastasis for treatment stratification of localised cancer

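### The planned late-event adjustment depends on how assumed late recurrences are split by CTC status; its premises favour CTC-positive men, so adjusted specificity would partly assume the hypothesis

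*Protocol*

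**What the plan says.** All of this is in Protocol section 7, Statistical considerations, unless stated otherwise.

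- **Hypothesis (2, Sample size).** CTC presence is expected to be almost perfectly sensitive and specific for micro-metastasis, and through it for treatment failure. Nearly all men with an observable biochemical recurrence are expected to be CTC-positive.
- **Expected specificity (2, Sample size).** It is predicted to be low, and the reason given is CTC-positive men who recur after the study window.
- **Premise of the adjustment.** "Assuming these events are due to micro-metastases at the time of surgery", the observed figures are to be used together with "additional analyses assuming up to 20% of the events occur after the funded 5-year project". The stated target is the real false positive rate and the real false negative rate.
- **Method of analysis (3).** Observed specificity and predictive values are reported at 4.5 years with a caveat that they may change. There is also to be an "additional analysis accounting for artificial inflation of false positives based on increasing prevalence of events".
- **Later data.** Section 6 foresees accuracy analyses at 7.5 and 10 years. Table 1 describes the 10-year metastasis endpoint as confirming that events have accumulated among the positives.

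Nowhere does the protocol say how the assumed late events are divided by CTC status.

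**The concern.** Late events are unobserved at the 5-year analysis, so the data cannot say which event-free men will have them. Adjusted sensitivity and specificity therefore depend on an allocation that the analyst supplies. The protocol leaves the allocation open but fixes premises that point one way: late events come from micro-metastases, CTCs mark micro-metastases, so late events belong to CTC-positive men. An adjustment run on that logic turns false positives into true positives because the hypothesis says so, and the result cannot then count as evidence for the hypothesis.

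The text considers no alternative in which a CTC-positive result is simply non-specific and late recurrences are unrelated to it. Calling the excess false positives artificial and the adjusted rates real tells the reader which figure to believe. This matters because the sample size section itself links specificity to a future in which a positive test could cost a man curative surgery, and section 2.2 (aim IV) intends the results to inform the design of an intervention trial.

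**Working it through.** **1. The plan's own figures.** The aim is to "confirm an expected sensitivity of 95% within 5% precision either side of a 95% confidence interval (CI"), with "the hypothesised prevalence of BCR events to be at least 40"%.

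- Events: 1.96² × 0.95 × 0.05 / 0.05² = 72.99, so 73.
- Patients: 73 / 0.40 = 182.5, so 183. This matches "requires at least 73 events, that is at least 183 recruited individuals".
- Inflation: 183 / (1 − 0.085) = 200. This matches "Inflate this by 8.5% to a target recruitment of 200".
- Specificity limit with 120 event-free men: 0.99 − 1.645 × √(0.99 × 0.01 / 120) = 0.975. The stated 97.5% reproduces as a one-sided 95% Wald limit.

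The starting table is therefore sound: 200 men, 80 events (40%), 120 event-free.

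**2. Inputs for the adjustment.**

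- True positives: 0.95 × 80 = 76 (protocol's expected sensitivity).
- Late events L: if 20% of all events are late, the total is 80 / 0.8 = 100, so L = 20.
- Observed false positives FP: **assumption**, since the protocol gives no count. The base case is 20, so observed specificity is 100/120 = 83.3%; a range follows.

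**3. Formulas.** Let p be the number of late events placed in CTC-positive men (p cannot exceed FP), and let TN = 120 − FP.

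- Adjusted sensitivity = (76 + p) / (80 + L)
- Adjusted specificity = (TN − (L − p)) / (120 − L)

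**4. Base case, FP = 20, L = 20.**

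- All in CTC-positives, p = 20: sensitivity 96/100 = 96%; specificity 100/100 = 100%.
- 95% in CTC-positives, p = 19: 95% and 99%.
- Unrelated to CTC status, p = 20 × 20/120 = 3.33: 79.33/100 = 79.3% and (100 − 16.67)/100 = 83.3%.
- All in CTC-negatives, p = 0: 76% and 80%.

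**5. Range over the assumed false positives** (sensitivity/specificity, L = 20).

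| FP | Observed | As many as possible CTC-positive | Unrelated to CTC | All CTC-negative |
|---|---|---|---|---|
| 10 | 95/91.7 | 86/100 | 77.7/91.7 | 76/90 |
| 20 | 95/83.3 | 96/100 | 79.3/83.3 | 76/80 |
| 30 | 95/75 | 96/90 | 81/75 | 76/70 |
| 40 | 95/66.7 | 96/80 | 82.7/66.7 | 76/60 |
| 60 | 95/50 | 96/60 | 86/50 | 76/40 |

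Specificity reaches 100% only when FP ≤ 20, that is, when observed specificity is at least 83.3%.

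**6. Other meaning of 20%.** If it means 20% of the 80 observed events, L = 16. In the base case the all-positive rule then gives 92/96 = 95.8% sensitivity and 100/104 = 96.2% specificity. Reaching 100% needs observed specificity of at least 104/120 = 86.7%.

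**7. Varying only the late fraction.** In the base case with all late events CTC-positive, late fractions of 0, 5, 10, 15 and 20% give specificity of 83.3, 86.4, 90.0, 94.4 and 100%. With late events unrelated to CTC status it stays at 83.3% throughout. A range over the fraction alone therefore does not show the dependence on allocation.

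**8. A test with no information.** With half of all men CTC-positive, TP = 40, FP = 60 and TN = 60. Assigning all 20 late events to positives gives (40 + 20)/100 = 60% sensitivity and 60/100 = 60% specificity, from 50%/50%. With late events unrelated to CTC status (p = 10) it stays at 50/100 = 50% and (60 − 10)/100 = 50%.

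**The case against.** The strongest reply is that the protocol does not state the allocation being criticised. That is correct. A detailed rule for a supplementary analysis may properly sit in a statistical analysis plan, so its absence is not the fault here. What stands is that the protocol has already fixed the explanation for low specificity, the origin of late events and the label on the result, and all three favour one allocation.

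A reader might infer that the plan lifts specificity to 100% by assumption. The text does not support that: 100% needs the unwritten all-positive rule and no more false positives than assumed late events. The protocol itself expects low specificity, and there the gain is smaller.

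A reader might also infer that the adjustment can only flatter the test. That goes too far as well, because the false negative rate is a stated target, which leaves room for late events in CTC-negative men. Naming it is not a safeguard, though: in the base case the all-positive rule also improves the false negative rate, from 5% to 4%.

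Finally, the observed estimates are already planned and caveated, the primary analysis is sensitivity, the late-event work is described as additional, and later follow-up analyses are foreseen. All of that stands and limits the weight of the point. It is also fair that short follow-up does misclassify some true later failures as false positives; the question is how many, and the 5-year data cannot answer it.

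**Conclusion.** The concern holds in limited form. The adjusted accuracy depends on an unstated split of unobserved events, and the protocol's premises lean towards the split that confirms its hypothesis. With 80 events, 76 true positives, 20 late events and an assumed 20 false positives, adjusted specificity runs from 80% to 100% and sensitivity from 76% to 96%, according to allocation alone. If late events are unrelated to CTC status, specificity does not move and sensitivity falls to 79.3%. These sizes rest on the assumed false positive count and on reading 20% as a share of all events; the ranges above show how they change.

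The documents do not show that the adjusted figure will replace the observed one, or that the primary sensitivity analysis is affected. The defect lies in the framing and in the missing no-association scenario for a secondary analysis. It is worth correcting because a reader could take the adjusted specificity as evidence when part of it is assumption.

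**What to change.** - Keep the planned observed sensitivity and specificity at 4.5 years as the headline.
- Call the late-event work a sensitivity analysis, and drop the descriptions of its output as real and of the excess false positives as artificial.
- State whether 20% refers to all events or to observed events.
- Vary the share of late events assigned to CTC-positive men from their observed share among event-free men (no information) up to 100%, with the number assigned limited to the false positives available. Cross this with the late fraction from 0 to 20%.
- Report adjusted sensitivity and specificity as pairs for every scenario, so that a gain in one is never shown without its effect on the other.
- State that the analyses already planned at 7.5 and 10 years will supersede this exercise.

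The cost is a few changed sentences and one small table, with no extra patients or data. The downside for the sponsor is a wider and less favourable range for the adjusted accuracy.

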	
To provide a preliminary assessment of the prognostic value of CTC data (positivity and gene expression) in predicting post-RP PCa metastasis development, overall survival and cancer specific survival.
 
To provide evidence and data which can be used to design a future clinical trial of a CTC- based intervention to be used to guide therapeutic choice in the management of high-risk localised PCa.
 
To evaluate the longer-term prognostic value of CTC detection and CTC gene expression for metastases and cancer-specific survival.
 
Primary endpoint
 
The primary outcome is post-RP treatment failure during the first 4.5 years of follow up from start of recruitment.
 
Post-RP treatment failure is defined as a PSA $\geq 0.2\text{mg/ml}$ at the routine PSA test 3 months after RP (commonly called 'failure to nadir') and remaining at this level or further increase afterwards without further treatment, or imaging detected appearance of cancer lesions.
 
Cancer lesions detected by imaging without a PSA rise might include neuroendocrine PCa and lesions detected by PSAM-PET. This combined post-RP treatment failure primary endpoint will maximally capture all the clinically significant cancer appearance events.
 
Secondary endpoints
 
BCR during the first 4.5 years of follow up: PSA $\geq 0.2\text{ng/ml}$ at any time post-RP and remaining at this level or further increase afterwards without further treatment.
 
Metastasis (any location)-free survival during the first 4.5 years of follow up. Only 5% of subjects with distant metastasis event (based on traditional imaging technologies) within this time frame (4-6).
 
Metastasis (any location)-free survival at 10 years follow up. to confirm that metastatic event rates have increased among the positives, i.e. a declining rate of "false positives".
 
Deaths from any cause during the first 4.5 years of follow up
 
Overall survival at 10 years of follow up.
 
Prostate cancer specific deaths during the first 4.5 years of follow up. Expected to be 2% or less based on previous studies in the post RP context.
 
Prostate cancer specific survival at 10 years of follow up. Our hypothesis is that most if not all of the patients dying of PCa will be in the CTC positive group.

Target sample size	294

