will be reported alongside the number of these participants with a positive by CTC result, and positive combined CTC result. Metastases-free, PCa-specific and overall survival will be reported during the 5 years study time frame and it is intended to perform a later analysis at 10 years of follow up. Preliminary investigation of the prognostic value of pre-surgery CTC data in terms of predicting survival outcomes will be investigated using Cox regression, with hazard ratios reported with associated 95% CIs. CTC data will be explored alongside other pre-surgery risk factors such as plasma PSA using multivariate analysis. Recurrence events and follow up CTC results will be reported and compared over time. The above analyses will be applied to the CTC gene panel. The gene panel will also be correlated with the pre- and post- RP CTC number changes and cancer progression events.

CTC results will be presented for the whole cohort who provided analysable blood samples and stratified by those included in the above analyses, and those excluded due to reasons such as a positive surgery margin, other evidence of locally remaining disease, and who subsequently have adjuvant ADT or radiotherapy.

8. Ethics

The study is a spin out project of the parent project authorised under RLTB ethics, where the main research tissue bank approval provided by the London City & East Research Ethics Committee.

9. Data handling, storage and record keeping- to describe who and how the data will be handled, which data nodes will be used, where it will be stored and security of the data

The CRF (funded by QMUL, but with contract at UCLH) will be part of the study management group and will act as the contact point between UCLH and QMUL. Under the MTA and data sharing agreement (DSA) between the two institutions and with patient consent, the CRF will collect blood samples during pre-surgery operation and after the surgery during the first PSA follow-up visit at UCLH.

The following clinical data will be collected for each patient by the CRF:

- Histology reports
- Clinical stage
- Prostate Specific Antigen (PAS) (pre- and post-surgery)
- Imaging (MRI, PSMA-PET/CT and bone scan)
- Results and record of adjuvant therapies
- Treatment date and method for post-surgery cancer recurrence

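### At 4.5 years the planned Cox hazard ratio for a binary CTC result will often have no finite estimate for prostate cancer death, and quite possibly none for metastasis; a penalised Cox model should be named

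*Protocol*

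**What the plan says.** Section 7 (Statistical considerations, 3) Method of analysis) names the outcomes: "Metastases-free, PCa-specific and overall survival will be reported during the 5 years study time frame". A later analysis at 10 years is intended. The prognostic value of pre-surgery CTC data for survival outcomes is to be examined "using Cox regression, with hazard ratios reported with associated 95% CIs", and the same analyses are to be repeated for the gene panel. The protocol calls this work preliminary. The same section also plans to report how many men had metastases, died of any cause or died of prostate cancer by 4.5 years, and how many of them were CTC positive.

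The expected event rates are in Section 3, Table 1, under secondary endpoints. For metastasis by 4.5 years: "Only 5% of subjects with distant metastasis event", a figure tied there to traditional imaging. For prostate cancer death over the same period: "Expected to be 2% or less based on previous studies in the post RP context". For prostate cancer-specific survival at 10 years: "Our hypothesis is that most if not all of the patients dying of PCa will be in the CTC positive group".

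Section 7, 2) Sample size, gives the other inputs: "The recruitment plan will be 200 patients in the first two years of the 5-year project"; "this study estimates predicting post-RP cancer events with 95% sensitivity"; and the hypothesis that "the presence of CTCs has close to 100% sensitivity and specificity for micro-metastasis, and thus RP treatment failure". The definitions in Section 7 make the gene-expression result and the combined CTC result binary.

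**The concern.** A Cox hazard ratio comparing CTC-positive with CTC-negative men needs at least one event in each group. If no CTC-negative man has an event, the partial likelihood keeps rising as the hazard ratio grows. The maximum-likelihood estimate is then infinite, and a Wald interval built from it carries no information.

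The protocol expects few metastases and very few prostate cancer deaths by 4.5 years, and it expects nearly all cancer events to be in CTC-positive men. So the promised result becomes harder to obtain the nearer the study hypothesis is to the truth. If this is met only at analysis, the substitute method will be chosen after the data have been seen.

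**Working it through.** **Reproducing the protocol's own figure.** Events needed to estimate 95% sensitivity to within 5 points either side: 1.96² × 0.95 × 0.05 / 0.05² = 72.99, so 73. Men needed at 40% prevalence: 73 / 0.40 = 182.5, so 183. Allowing for 8.5% loss: 183 / 0.915 = 200. The stated 73, 183 and 200 all reproduce.

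**Expected events by 4.5 years in 200 men** (rates from Table 1):
- Distant metastasis: 0.05 × 200 = 10.
- Prostate cancer death: 0.02 × 200 = 4 at most.
- Biochemical recurrence, for contrast: 0.40 × 200 = 80.

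**Chance of no event among CTC negatives.** With D events, each CTC positive with probability s, the chance is s^D. At s = 0.95:
- Prostate cancer death: 0.95^4 = 0.81. With 2 deaths, which the protocol's rate allows, 0.95^2 = 0.90.
- Metastasis: 0.95^10 = 0.60.
- Biochemical recurrence: 0.95^80 = 0.017.

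Letting the event count vary gives nearly the same: (1 − 0.02 × 0.05)^200 = 0.82 for prostate cancer death and (1 − 0.05 × 0.05)^200 = 0.61 for metastasis.

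**Varying the assumptions.**

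| Setting | Prostate cancer death | Metastasis |
|---|---|---|
| s = 0.90, 200 men | 66% | 35% |
| s = 0.95, 200 men | 81% | 60% |
| s = 0.98, 200 men | 92% | 82% |
| s = 1.00, 200 men | 100% | 100% |
| s = 0.95, 294 men (6 deaths, 15 metastases) | 74% | 46% |

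If metastases at any location, or those seen on PSMA-PET, raise the metastasis count, then at s = 0.95 the chance is 0.95^20 = 0.36 with 20 events and 0.95^30 = 0.21 with 30.

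**What the Cox model does then.** In a constructed data set of 200 men, 80 of them CTC positive, with 10 events all in positives, the log partial likelihood was −51.24 at a log hazard ratio of 0, −43.52 at 2, −41.79 at 4 and −41.496 at 20. It rises throughout and levels off, so there is no finite maximum.

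Some inference survives. The likelihood-ratio statistic approaches 2 × (51.24 − 41.496) = 19.5 on 1 degree of freedom. The 95% profile lower limit lies where the log-likelihood equals −41.496 − 1.92 = −43.42. That is just above a log hazard ratio of 2, a hazard ratio a little over 7.4. There is no upper limit.

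**If one event does fall in the negatives.** A constructed example with 1 event in negatives and 9 in positives gave a hazard ratio of 13.6 (95% CI 1.7 to 107). At s = 0.95 the chance of no event or one event in negatives is 91% for metastasis and 99% for prostate cancer death.

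**The case against.** The strongest reply is that the protocol names only a model class. It does not say Wald, it does not exclude penalised estimation, and the choice of estimator under sparse data is often left to the statistical analysis plan, which is not at hand. The first two parts are true. The protocol does, however, fix the form of the result, a hazard ratio with a 95% CI, for outcomes where its own figures say the usual estimate will often not exist. So this is more than missing detail.

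Several narrower objections also stand:
- Event counts by CTC result are already planned. They are the natural display when negatives have no events, though they do not supply the promised hazard ratio.
- The 5% is for distant metastasis on traditional imaging, while the endpoint covers any location and follow-up imaging includes PSMA-PET. If deaths count as events in metastasis-free survival, a death from another cause in a CTC-negative man removes the separation.
- The statement that most or all prostate cancer deaths will be CTC positive belongs to the 10-year endpoint. The 95% sensitivity is for post-RP cancer events, mostly biochemical recurrence. Using it for metastasis and prostate cancer death is an assumption.
- CTC enumeration is also collected, and a count need not separate the events as a binary result can.

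A reader might infer that the whole prognostic analysis fails, or that no inference at all is possible. The documents support neither. A likelihood-ratio test and a one-sided profile bound remain, and biochemical recurrence has only a 1.7% chance of the problem at 95% sensitivity. Overall survival is not clearly affected. The protocol gives no all-cause death rate, but assuming 1% to 5% other-cause deaths in 80 to 118 CTC-negative men, the chance of none runs from 0.99^80 = 0.45 down to 0.95^118 = 0.002.

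**Conclusion.** The point holds for a binary CTC result, in the 4.5-year analysis, for prostate cancer-specific survival and, less firmly, for metastasis. On the protocol's inputs there is about an 81% chance that the maximum-likelihood hazard ratio for prostate cancer death is infinite, and about 60% for distant metastasis. These figures rest on 200 analysed men, the Table 1 event rates, and 95% sensitivity carried over to these two outcomes. The metastasis figure is the softer one, because more events or counted deaths would lower it.

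It would be wrong to read this as a threat to the primary analysis: the estimate of sensitivity for treatment failure does not use the Cox model. Nor can the size be carried to 10 years, because the protocol gives no 10-year event rates. The analysis concerned is secondary and described as preliminary, so the priority is low to moderate.

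**What to change.** In Section 7, 3) Method of analysis, add that for prostate cancer-specific death and for metastasis the hazard ratio for binary CTC results will be estimated by Firth-penalised Cox regression with profile penalised-likelihood 95% CIs. Present it beside the event counts by CTC result already planned, and add cumulative incidence by CTC group. The penalty keeps the estimate and both limits finite when one group has no events.

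The cost is a change of wording: no new patients, data or endpoints, and the method is in standard software. The drawback is slight shrinkage of the estimate towards no effect. It does not create information, so with about 4 to 10 events the intervals will stay wide. How many covariates to explore alongside the CTC result can be left to the analysis plan.
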